3.2 Number of Subjects

400 study subjects will receive vaccination with the Janssen Ad26.CoV2.S vaccine in Segment I. We will enroll and screen up to 1200 patients to achieve this number of vaccinated subjects expecting that up to 800 patients will have anti-SARS-CoV-2 spike antibody levels at the time of screening. Approximately 800 patients that will not receive the Janssen Ad26.CoV2.S vaccine will be followed for outcomes such as COVID infections up to 2 years. Up to 250 subjects in Segment I might participate in Segment II.

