	
Secondary Objectives
 
 1. To determine the response* of the Janssen Ad26.CoV2.S vaccine in the subset of subjects who did not respond to an additional dose of the Janssen Ad26.CoV2.S vaccine in Segment I while on their maintenance immunosuppression. In this instance immunosuppression is adjusted (Segment II). 2. To determine the incidence of COVID-19 infection up to 2 years after enrollment or additional dose in all enrolled kidney transplant recipients (received Janssen Ad26.CoV2.S vaccine or not). 3. To determine the safety of an additional dose with the Janssen Ad26.CoV2.S vaccine after two or more doses of mRNA vaccine including vaccination with or without immunosuppression adjustment. 
*Response is defined as achieving an anti-SARS-CoV-2 spike protein antibody level ≥ 250 U/ml 28 days after an additional dose with the Janssen Ad26.CoV2.S vaccine.

	
Exploratory Objective
 
 1. To perform exploratory in vitro assays to better understand the mechanisms of response to COVID-19 vaccination.
Number of Subjects	Up to 1200 kidney transplant recipients at least 90 days after transplantation. 400 patients with low or no anti-SARS-CoV-2 spike protein antibody levels will receive one or two additional doses of the Janssen Ad26.CoV2.S vaccine per protocol. Approximately 800 kidney transplant recipients who had a good response to mRNA vaccines will be followed for 2 years for COVID infection and other outcomes.
Diagnosis and Main Inclusion	Kidney transplant recipient who have previously received two or more COVID-19 vaccinations (either the Pfizer or Moderna vaccines).
Study Product, Dose, Route, Regimen	
Janssen Ad26.CoV2.S, vaccine. The Janssen Ad26.COV2.s vaccine will be supplied at a concentration of 1×10^{11} vp/mL in single-use vials, with an extractable volume of 0.5 mL, and dose at 5×10^{10} vp. All participants will receive a single 0.5 mL dosage, typically in the deltoid.
 
Segment I—one dose Segment II—two doses (see protocol)

Duration of Administration	Each dose will be a single dose of Janssen Ad26.CoV2.S vaccine
Reference therapy	No

Statistical Methodology	A chi-square test will be used to assess whether there is a statistically significant difference in the response rate for subjects receiving an additional dose with the Janssen Ad26.CoV2.S vaccine either with immunosuppression reduction (N = 150) or without reduction (N = 150).

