As of August 2021, more than 400 anti-SARS-CoV2 spike protein antibody tests had been performed in the Mayo Clinic solid organ transplant recipient population. Of these, 245 were in patients with documented vaccination post-transplantation. The time from vaccination to anti-SARS-CoV-2 spike protein test averaged 72 days (Range 1-181d) The majority of recipients had no response (51%) or had a low-level response (<250 U/ml, 33%). Only 16% had a value ≥ 250 U/mL of anti-SARS-CoV-2 spike protein antibody.

Post-Vaccination Spike protein result			
No_Responder	<250 U/ml	>250 U/ml	Total
125	81	39	245
51%	33%	16%	100%

In stark contrast to the response rate to the COVID-19 vaccine series post-transplant, if a recipient received vaccination prior to transplant, then 61% (1423) of patients had a response ≥ 250 U/ml. Nine patients had a low response (<250 U/mL) with 3 between 50-250 U//ml and 6 <50 U/ml). These data are similar to the overall Mayo Clinic patient cohort tested to date. Among >3800 anti-SARS-CoV-2 spike protein antibodies test results 56% of patients have a value ≥ 250 U/ml by 28 days post-vaccination.

COVID Infections and Deaths

Recent studies have suggested that solid organ transplant recipients have 4 times the rate of death after COVID infection compared to the general population (reviewed by Osmanodja et al[15]) suggesting that transplant recipients have mortality rate with COVID infection 4 times that of otherwise healthy people. At Mayo, the overall known mortality rate has been 3.8% compared to a

mortality rate of 0.8% in the general population—almost exactly the 4 time observed in other studies.

As of August 1, 2021, using the Mayo clinic COVID data registry, we identified 25 patients with breakthrough infection despite re-vaccination. Nine patients required oxygen therapy, 1 required mechanical ventilation support and 1 ECMO. None of the fully vaccinated individuals have died. [16]

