3.1.3 Responders to mRNA Vaccination

Those participants who were determined to have an initial response to either the Pfizer or Moderna vaccine series (defined as having a screening SARS-CoV-2 spike protein antibody result ≥ 250 U/mL) will not be offered the Janssen Ad26.CoV2.S vaccine. Participants will continue to be followed for approximately 2 years so their information can be used as a comparison for Segments I and II. These participants will be followed for 2 years for clinical outcomes (COVID infections, graft and patient survival). During this time their medical information will be collected, both through medical chart review and by the study team, and Mechanistic Studies will be performed (in a subset of subjects).

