4.3 Subject Recruitment, Enrollment and Screening

Kidney transplant recipients who have received at least two of the mRNA vaccines will be identified by review of their medical record to see if they preliminary fit other inclusion/exclusion criterion for the study. If they appear to be a potential subject they will be contacted via phone or the Mayo Clinic portal to determine interest in study participation. If the potential participant is interested, they will be consented in person or remotely and instructed on study procedures.

Consented subjects will submit a blood sample to determine if they fit the enrollment criterion for the anti-SARS-CoV-2 spike protein level (<250U/ml). Those with an anti-SARS-CoV-2 spike protein levels at <250U/ml will receive the Janssen Ad26.CoV2.S vaccine.

This study plans to enroll up to 1200 research subjects to obtain 400 that have low or no detectable anti-SARS-CoV-2 spike protein antibody levels. Based on prior small studies, we expect (conservatively) that at least 20% will have low, but detectable antibody levels and 30% of all patients will have no detectable levels and will meet this inclusion criteria and other inclusion criteria. Thus, we envision screening approximately 1,200 kidney transplant recipients. Screening will be completed once 400 subjects have enrolled in Segment I.

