6.8 Statistical Methods

In general, univariate descriptive statistics will be calculated, as appropriate for all variables including baseline values for demographic, clinical, and outcome variables. These variables will be summarized across treatment groups as well as strata of baseline antibody levels (none versus low) and compared for possible confounding of the primary and secondary comparisons. For example, what are the univariate and multivariate factors related to the initial good response to mRNA vaccination—data collected at the time of enrollment in all 1200 study subjects. Of additional interest are factors related to response to receiving the Janssen Ad26.CoV2.S vaccine as well as developing COVID infection at 2 years.

The **primary comparison (randomized trial of immunosuppression adjustment)** will focus on a chi-square test of vaccination response between those patients that did not have reduced immunosuppression versus those that did have a change in immunosuppression. Only the patients with a zero (undetectable) antibody level at the time of study enrollment will be compared.

Other analyses will focus on the overall incidence rate of reaching the primary endpoint across all patients or stratified by antibody levels (zero or low) at the time of screening. These analyses will be carried out using one-sample or two-sample chi-square tests. In addition, there is interest if possible confounding variables have any impact on reaching the primary endpoint. These analyses will focus on univariate and multivariate logistic regression models of binary response based on possible confounding variables.

Studying the durability of antibody production will utilize longitudinal analyses such mixed effects models to account for multiple (correlated) observations from the same individual. Assumptions of these models will be assessed through the residual plots.

Finally, we are interested in assessing changes in infection rate and cause-specific mortality during follow-up. We will analyze time to infection or COVID-related death using standard survival analysis procedures such as Kaplan-Meier estimation and Cox regression.

Handling of Missing Data

Queries in the Medidata Rave system will be used to identify outliers as well as missing and inconsistent data entered into the system. An example would be dates that appear out of order such as a death prior to an infection.

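### The planned cohort of about 800 initial responders exceeds what the plan's own screening rates can deliver: at most 400 to 600

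*Combined protocol and SAP*

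**What the plan says.** The size of the unvaccinated cohort is given in several places.

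- Study Summary, Number of Subjects: "Approximately 800 kidney transplant recipients who had a good response to mRNA vaccines will be followed for 2 years". This identifies the 800 as responders.
- Section 3.1.4: the mechanistic subset of initial responders is described as 50 out of 800.
- Section 3.2: "We will enroll and screen up to 1200 patients to achieve this number of vaccinated subjects", and then "Approximately 800 patients that will not receive the Janssen Ad26.CoV2.S vaccine will be followed for outcomes such as COVID infections up to 2 years". The second sentence defines the group by not being vaccinated. Section 3.2 also gives 800 as a maximum for patients with antibody at screening.
- Section 6.9: at most 800 patients at 250 U/mL or more, again worded as a ceiling.

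Section 4.3 gives the screening yield: "at least 20% will have low, but detectable antibody levels and 30% of all patients will have no detectable levels". It calls these expectations conservative and says that these patients also meet the other inclusion criteria. It then sets the stop: "Screening will be completed once 400 subjects have enrolled in Segment I". Section 3.1.1 divides the 400 into 300 non-responders and 100 low responders.

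Section 3.1.3 follows the responders so that "their information can be used as a comparison for Segments I and II", and section 6.3 repeats this use. Section 6.8 plans an analysis of factors related to a good mRNA response on "data collected at the time of enrollment in all 1200 study subjects".

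**The concern.** The figure of 800 appears to be 1,200 minus 400. As a count of responders it needs two thirds of screened patients to be at 250 U/mL or more, whereas section 4.3 expects half at most. The Study Summary and section 4.3 cannot both be right.

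At stake is the precision of a secondary, non-randomized comparison: 2-year COVID infection, graft survival and patient survival in initial responders against Segments I and II. The predictor analysis in section 6.8 would also have fewer subjects than stated if screening ends before 1,200. A reader who takes 800 at face value will expect tighter intervals than the design can give.

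**Working it through.** **Inputs.** Cap on screening 1,200 and Segment I target 400 (section 3.2); low share at least 0.20 and undetectable share 0.30 (section 4.3); targets of 300 non-responders and 100 low responders (section 3.1.1).

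**Step 1: the plan's figure.** 1,200 − 400 = 800. Implied responder share: 800 / 1,200 = 66.7%. Implied share below 250 U/mL: 400 / 1,200 = 33.3%.

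**Step 2: the share implied by section 4.3.** Responders are at most 1 − 0.20 − 0.30 = 0.50. The low share is worded as a minimum, so 0.50 is an upper limit under the plan's rates.

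**Step 3: expected responders = screened × 0.50.**

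| Screening ends when | Screened | Responders (at most) | Shortfall from 800 |
|---|---|---|---|
| any 400 are in Segment I | 400 / 0.50 = 800 | 400 | 50% |
| 300 non-responders are found | 300 / 0.30 = 1,000 | 500 | 37.5% |
| the cap is reached | 1,200 | 600 | 25% |

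Reaching 800 responders at these rates needs 800 / 0.50 = 1,600 screened, which is above the cap.

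**Step 4: the stop rule against the two targets.** At 800 screened, expected non-responders are 0.30 × 800 = 240, which is 60 short of 300. Expected low responders are 0.20 × 800 = 160, which is 60 above 100. Filling both targets takes 1,000 screened.

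**Step 5: can 800 unvaccinated patients be reached another way?** At 1,200 screened, expected counts are 600 responders, 360 non-responders and 240 low responders. Taking 300 and 100 into Segment I leaves 600 + 60 + 140 = 800 unvaccinated, of whom 200 are below 250 U/mL.

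**Step 6: the predictor analysis in section 6.8.** At 1,000 screened it has 200 / 1,200 = 17% fewer subjects than stated. At 800 screened it has 400 / 1,200 = 33% fewer.

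**Step 7: effect on precision (illustration).** Assume that responders are infected at 7% per year. The 2-year incidence is 1 − 0.93² = 13.5%, and the 95% half-width is 1.96 × √(0.135 × 0.865 / n):

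| Responders | Half-width (percentage points) |
|---|---|
| 800 | 2.4 |
| 600 | 2.7 |
| 500 | 3.0 |
| 400 | 3.3 |

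**Step 8: sensitivity to other shares in section 1.3, all at 1,200 screened.** 16% gives 192, 56% gives 672 and 61% gives 732. None reaches 800.

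**The case against.** Three points can be made for the plan.

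1. Section 3.2 speaks of patients who do not receive the vaccine, not of responders, and section 3.3 follows all screened patients who are not vaccinated. Step 5 shows that 800 unvaccinated patients is attainable at 1,200 screened. This stands for that sentence taken alone. It works only by counting 200 patients below 250 U/mL, beyond the Segment I targets. The Study Summary calls the group good responders. Section 4.3 says that patients below 250 U/mL will be vaccinated and ends screening at 400 in Segment I, and neither place describes an unvaccinated surplus.

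2. Sections 3.2 and 6.9 also give 800 as a ceiling, and an expected count below a ceiling does not contradict it. This stands in full. The conflict is with the approximate figure in the Study Summary, the denominator in section 3.1.4 and the 1,200 in section 6.8.

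3. No planned test is sized on 800. Section 6.7 powers the randomized comparison on 150 per arm. The 2-year calculations in section 6.8 are one-sample tests against historical rates, with 400 patients for infection. This also stands, and it limits the consequence. The subset of 50 responders in section 3.1.4 remains feasible in every scenario above.

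**Conclusion.** The stated cohort of about 800 initial responders does not follow from the plan's screening rates, which allow at most 400, 500 or 600 depending on when screening ends. The comparison group is 25% to 50% smaller than stated. This rests on taking the section 4.3 rates as they stand and on expected counts, without sampling variation. The point is one of internal consistency and planned precision; it does not touch the primary result.

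Four stronger readings are tempting and are not supported:

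- A reader might infer that the comparator is always half the stated size or less. At the plan's rates that holds only if screening stops at any 400; the other cases give 62.5% and 75% of 800.
- A reader might infer that nothing in the documents can produce 800. That is true of responders at the plan's rates, but not of unvaccinated patients at 1,200 screened.
- A reader might take the 16% in section 1.3 as the forecast. Those 245 tests cover all solid organ recipients vaccinated after transplant, taken 1 to 181 days after vaccination. The trial enrols kidney recipients more than 28 days after their latest dose, some with three doses, and does not require vaccination after transplant. The same section also reports 56% and 61% in other groups. All three are sensitivity figures only.
- A reader might infer that a planned test loses its power. The plan prints no such test. Suppose 400 vaccinated patients at 10% per year were compared with responders at 7% per year over 2 years (two-sided 5%, two-proportion approximation). Power would be about 0.69 with 800 responders, 0.64 with 600, 0.61 with 500 and 0.56 with 400. It would be modest even at the stated size, so the shortfall does not by itself create the risk of over-reading a null result.

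**What to change.** - In the Study Summary and sections 3.1.4, 3.2 and 6.9, restate the expected number of initial responders as at most about 500 (1,000 screened, the number needed for 300 non-responders), and at most 600 if all 1,200 are screened.
- In section 6.8, replace the reference to 1,200 subjects by all enrolled subjects, with about 1,000 to 1,200 expected.
- In section 4.3, reconcile the stop rule with the 300 and 100 targets, since stopping at any 400 gives about 240 non-responders at the plan's rates. State whether responders continue to be enrolled once Segment I is full, and how patients below 250 U/mL beyond the targets are classified and counted.
- Report the responder contrast as estimates with confidence intervals, and give the expected interval width at the restated size.

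These are wording changes and need no patients beyond the present cap. The cost is that the stated cohort size and precision become less favourable.

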3.3 Duration of Participation

Subjects who only participate in Segment I will be followed for 2 years after receiving the Janssen Ad26.CoV2.S vaccine. Those who participate in Segment II will have their participation extended, with 2 years of clinical follow up after receiving the second Janssen Ad26.CoV2.S vaccine date. Screened patients not receiving the Janssen Ad26.CoV2.S vaccine will be followed for 2 years.

3.4 Primary Study Endpoints

The primary endpoint of all studies is the detection of antiSARS-CoV-2 spike antibody levels ≥ 250 U/ml in serum 28 days after receiving the Janssen Ad26.CoV2.

We have dual primary objectives in this study with the response defined as the following: achieving an anti-SARS-CoV-2 spike protein antibody level ≥ 250 U/ml 28 days after an additional dose with the Janssen Ad26.CoV2.S vaccine.

1. To assess whether an anti-SARS-CoV-2 spike protein antibody level of ≥ 250 U/mL can be achieved 28 days after a dose of the Janssen Ad26.CoV2.S vaccine in kidney transplant recipients who did not form acceptable levels of anti-SARS-CoV-2 spike protein antibody (<250 U/ml but >0 U/mL) after receiving two or more doses of a mRNA vaccine: Pfizer-BioNTech (BNT162b2 vaccine) or Modena (mRNA-1273). This includes any combination of the Pfizer-BioNTech (BNT162b2 vaccine) or the Moderna (mRNA-1273) results in two or more doses of mRNA vaccine. This is not randomized and not controlled.
2. To compare whether a dose of the Janssen Ad26.CoV2.S vaccine can achieve an anti-SARS-CoV-2 spike protein level ≥ 250 U/mL in kidney transplant recipients with no detectable anti-SARS-CoV-2 spike protein antibody after two or more mRNA vaccines. Kidney transplant recipients will be randomized to either maintenance of current immunosuppression or

adjustment in immunosuppression around the time of receiving the Janssen Ad26.CoV2.S vaccine. The number of subjects with anti-SARS-CoV-2 spike protein level ≥ 250 U/mL between the two randomized groups will be compared.

Thus, the ***primary comparison*** for this study is the rate of achieving this endpoint after receiving the Janssen Ad26.CoV2.S vaccine in patients who: 1) had undetectable anti-SARS-CoV-2 spike protein antibody levels after 2 or more doses of mRNA vaccine; and then were 2) randomized to either no alteration in immunosuppression vs alteration in immunosuppression around the time of receiving the Janssen Ad26.CoV2.S vaccine. The power calculations will focus on the difference in the proportion of patients who meet this endpoint between those with no alteration and those with an alteration in immunosuppression.

3.5 Secondary Study Assessments/Endpoints

- Any response in non-responders: Number and percentage of patients with undetectable anti-SARS-CoV-2 spike protein antibody level after 2 or more doses of mRNA vaccine who receive the Janssen Ad26.CoV2.S vaccine who develop anti-SARS-CoV-2 spike protein antibody levels >0 or <250 at 28 days.
- Good response in low-responders: Number and percentage of patients with anti-SARS-CoV-2 spike protein antibody levels >0 but <250 U/ml after 2 or more doses of mRNA vaccine who receive the Janssen Ad26.CoV2.S vaccine who develop anti-SARS-CoV-2 spike protein antibody levels ≥ 250 at 28 days.
- Segment II. Rate of achieving an anti-SARS-CoV-2 spike protein antibody level ≥ 250 U/ml 28 days after receiving the Janssen Ad26.CoV2.S vaccine in patients who failed to achieve the response in Segment I who received a second dose of the Janssen Ad26.CoV2.S vaccine after adjustment of immunosuppression.
- Durability of anti-SARS-CoV-2 spike protein antibody levels in patients who developed any level of antibody response after receiving the Janssen Ad26.CoV2.S vaccine at 180 days and/or between 1 and 2 years after receiving the Janssen Ad26.CoV2.S vaccine.
- Incidence of COVID-19 infection at 2 years.

Exploratory Endpoints (Mechanistic studies):

Baseline Differences

It is expected that at baseline (prior to receiving the Janssen Ad26.CoV2.S vaccine), when compared to responders, low responders and non-responders will demonstrate no SARS-CoV-2 specific T and B cells and lower mean number of T cell receptors. Non-responsiveness will correlate with lower mean numbers of T and B cells including specific subtypes such as T-helper cells and memory B cells.

Response to Alterations in Immunosuppression

Alterations in immunosuppression will lead to increased number of T and B cells from baseline. Paired t test with each patient serving as their own controls.

Additional Dose with the Janssen Ad26.CoV2.S Vaccine

Compared to those who do not respond, patients who respond to receiving the Janssen Ad26.CoV2.S vaccine will demonstrate new or increased levels of SARS-CoV-2-specific T and B cells. They also will have higher baseline levels of T cells, B cells, serum immunoglobulin levels and T cell repertoire.

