This study is a phase III, prospective, open label clinical trial with one randomized arm. Its goal is to meet the unmet clinical need to provide vaccine induced immunity for our immunocompromised kidney transplant patients after receiving two or more doses of the Pfizer or Moderna COVID-19 vaccine (see Figure below for overview). Subjects will be pre-screened and interested qualified

subjects will be offered participation in this trial and, if applicable, consented. Once consented, serum levels of anti-SARS-CoV-2 spike protein antibody will be obtained. Patients with levels ≥ 250 U/ml will be followed for two years without receiving the Janssen Ad26.CoV2.S vaccine for clinical outcomes (COVID infection, graft and patient survival).

Study Schematic: Augmenting Anti-COVID Immunity In Transplant Recipients Via Heterologous Prime Booster Vaccination With Janssen Ad26.CoV2.S Vaccine

*Clinical endpoints include COVID-19 infection (primary endpoint) and secondary endpoints (hospitalization, infectious complications, patient survival, graft survival, significant AEs related to vaccine or to reduction in immunosuppression, de novo alloantibody)

** Exact cut-off still to be determined

Segment I

Patients with levels >0 but <250 U/ml of anti-SARS-CoV-2 spike protein antibody levels will receive one dose of the Janssen Ad26.CoV2.S vaccine. Their anti-SARS-CoV-2 spike protein antibody levels will be measured at multiple time points after receiving the Janssen Ad26.CoV2.S vaccine. Patients with undetectable anti-SARS-CoV-2 spike protein antibody levels (i.e. with levels = 0) will be randomized 1:1 (stratified by the number of mRNA doses received 2 vs 3) to receive the Janssen Ad26.CoV2.S vaccine and either: 1) continue on their current immunosuppression regimen or 2) have a transient immunosuppression medication adjustment prior receiving the Janssen Ad26.CoV2.S vaccine (described in Section 5.2.1).

Segment II

Patients in Segment I who received Janssen Ad26.CoV2.S vaccine while maintained on their usual immunosuppression medication dosage and did not reach the anti-SARS-CoV-2 spike protein antibody endpoint (≥ 250 U/ml) at 28 days will be offered an additional Janssen Ad26.CoV2.S vaccination. In this segment, immunosuppression will be adjusted (as described in Section 5.2.1)

and anti-SARS-CoV-2 spike protein antibody levels will be assessed at 28 days after the second vaccination with the Janssen Ad26.CoV2.S vaccine as the primary endpoint.

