6.1.5 Days 14 (+/- 7 Day) and 28 (+/- 7 Days)

Anti-SARS-CoV-2 spike protein antibody and anti-SARS-CoV2 nucleocapsid total antibody levels will be obtained during these study event periods. Study team will record any changes to concomitant and immunosuppressant medications or therapies, as well as changes to health status to determine any potential adverse events. Blood will be collected for a platelet count and for mechanistic studies (Day 28 only). After Day 28, subjects randomized to a change in their immunosuppression medication will revert back to their original regimen. COVID-19 symptoms will be assessed to determine if the subject has experienced any COVID-19 symptoms or recently been tested. Patient and graft status information will also be collected. The study team will review and complete the safety follow up questionnaires with the subject.

If necessary, a symptom directed physical exam can be performed.

Segment II (described in Section 6.2) will begin on Day 28 for individuals whose immunosuppression regimen was not changed and continue to have low to no response levels for their COVID-19 spike protein test.

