6.7 Sample Size Determination

In the study populations, the actual response rates to receiving the Janssen Ad26.CoV2.S vaccine is not known.

We base our statistical calculations on what is suggested by the existing small, non-randomized reports in the current literature. For example, Kamar et al reported that 26/59 (44%) seronegative patients after two doses became seropositive after a third dose [8]. However, it appears that 17 of the 26 still had anti-S antibody titers <200. Thus, the response rate given the endpoint that we plan for this study (≥ 250 U/ml) would be 9/44 (20%) for those with no antibodies prior to receiving the Janssen Ad26.COVID-19 vaccine and 60% for those with low, but non-zero, levels of antibody prior to receiving the Janssen Ad26.COVID-19 vaccine.

The primary endpoint for our study is a measured anti-S antibody level of ≥ 250 U/ml. Power calculations are based on the comparison at the end of Trial Segment I using a two-sample, two-tailed test of the difference in two proportions. This focuses on whether or not there is a statistically significant difference in the proportion of responders between those patients who had zero antibodies at the time of receiving the Janssen Ad26.COVID-19 vaccine with an adjustment in immunosuppression (N = 150) and those without an adjustment in immunosuppression (N = 150). Effect sizes are based on the square-root arcsine transformation.

Trial Segment I

These power calculations pertain to the randomized arm of **Segment I involving immunosuppression adjustment**: kidney transplant recipients with anti-SARS-CoV-2 spike protein antibody levels = 0 at baseline (i.e. after receiving 2 or more doses of mRNA vaccine) who are randomized to be maintained on their current immunosuppression vs transient immunosuppression adjustment around the time of receiving the Janssen Ad26.CoV2.S vaccine (n=150/arm).

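### The secondary endpoint for any response in non-responders is met by every Day 28 result as written, and the plan does not settle whether levels of 250 U/mL or more count

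*Combined protocol and SAP*

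**What the plan says.** The first bullet of Section 3.5 opens "Any response in non-responders: Number and percentage of patients with undetectable anti-SARS-CoV-2 spike protein antibody level" and counts the vaccinated patients in that group "who develop anti-SARS-CoV-2 spike protein antibody levels >0 or <250 at 28 days". Three other places bear on its meaning.

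- The next bullet in Section 3.5 describes the baseline band for low responders as "patients with anti-SARS-CoV-2 spike protein antibody levels >0 but <250 U/ml after 2 or more doses of mRNA vaccine". There the two bounds are joined by *but*, so both must hold.
- The durability bullet in Section 3.5 concerns antibody levels "in patients who developed any level of antibody response after receiving the Janssen Ad26.CoV2.S vaccine", with no upper bound.
- Section 3.4 defines response for the primary objectives only as 250 U/mL or more at 28 days. For the randomised comparison it states: "The number of subjects with anti-SARS-CoV-2 spike protein level ≥ 250 U/mL between the two randomized groups will be compared".

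The baseline group is set out under Segment I in Section 3: "Patients with undetectable anti-SARS-CoV-2 spike protein antibody levels (i.e. with levels = 0) will be randomized 1:1". Neither Section 6.8 (statistical methods) nor Section 6.9 (analysis populations) defines the any-response endpoint or says how levels of 250 U/mL or more are treated in it.

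**The concern.** An endpoint that every tested patient meets cannot distinguish a patient who made antibody from one who did not. An analyst will have to repair it, and there are two natural ways to do so.

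- **Any detectable level (above 0, no upper bound).** This fits the label and the durability bullet.
- **Intermediate band (above 0 and below 250).** This explains why an upper bound was written at all, and it matches the neighbouring bullet.

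Under the band reading, an endpoint called any response would exclude exactly the patients who meet the protocol's own definition of response. The exclusion would also be unequal between the randomised arms, because the plan expects more patients in the adjustment arm to reach 250 U/mL. The trial is open label (Sections 5.8 and 7.4), so a choice left until analysis could be made with results by arm in view.

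**Working it through.** The plan gives no expected rate, test or power for this endpoint, so there is no stated figure to reproduce. The check has three parts.

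**1. Logic of the written rule.** Let x be the Day 28 level. The rule is x > 0 or x < 250.

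| x (U/mL) | x > 0 or x < 250 (as written) | x > 0 | x > 0 and x < 250 |
|---|---|---|---|
| 0 | met | not met | not met |
| 0.4 | met | met | met |
| 100 | met | met | met |
| 249.9 | met | met | met |
| 250 | met | met | not met |
| 5000 | met | met | not met |

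The written rule returns 100% of patients with a result. The two repairs disagree only at 250 U/mL and above.

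**2. The plan's own literature example.** Section 6.7 cites a report in which "26/59 (44%) seronegative patients after two doses became seropositive after a third dose", and adds that 17 of those 26 had titres below 200. That study gave a third mRNA dose and the cut is 200, so this is illustration only.

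- As written: 59/59 = 100%
- Any detectable level: 26/59 = 44.1%
- Band: 17/59 = 28.8%
- Converters left out by the band: 26 − 17 = 9, and 9/26 = 34.6%

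Section 6.7 puts the high-titre share at 9/44, or 20%. Subtracting that 20% from 44% would give a band figure of about 24% instead.

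**3. Patients left out by the band in this trial.** Assume 150 per arm, all with a Day 28 result. If p_c and p_a are the proportions reaching 250 U/mL or more without and with adjustment, the number left out is 150·p_c + 150·p_a and the share of 300 is (p_c + p_a)/2.

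- Plan's expectation, 20% and 60%: 30 + 90 = 120, and 120/300 = 40%
- Power-table row 20% and 37%: 30 + 55.5 = 85.5, and 85.5/300 = 28.5%
- Lowest power-table row, 10% and 24%: (10 + 24)/2 = 17%
- Highest power-table row, 63% and 80%: (63 + 80)/2 = 71.5%

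At 20% and 60% the band percentage cannot exceed 100 − 20 = 80% without adjustment or 100 − 60 = 40% with it. These are ceilings, not forecasts, because the documents give no any-response rate for the adjustment arm.

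**The case against.** The strongest reply is that nobody would report 100%. The sentence counts patients who develop antibody, under a label that contrasts any response with the good response of the next bullet, so a patient who stays at 0 is excluded by plain sense. Label, verb and durability bullet all lean towards any detectable level. Even on the band reading little is lost: patients at 250 U/mL or more are counted in the primary endpoint, so adding the two counts recovers the any-detectable figure. The endpoint is descriptive, and entry to Segment II does not use it.

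Much of this stands. The 100% shows faulty drafting and is not a likely result. Most power-table rows are detectable-difference scenarios, so only 20% and 60% represents the plan's expectation. The patients left out by the band would still appear elsewhere in the report.

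It does not remove the defect. The written upper bound and the neighbouring bullet keep the band reading open, and no section closes it. Recovering one figure from the other also needs matching denominators. Section 6.9 uses the all-completed population for the primary analysis and the broader all-treated population for secondary analyses, so they may differ.

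**Conclusion.** The concern holds. The endpoint rule is wrong as written, and its two natural repairs give materially different percentages: they differ by 40 percentage points of the 300 non-responders at the plan's expected rates, and by 17 to 71.5 points across the power-table rows. These figures assume 150 patients per arm with complete Day 28 results. The literature example (100%, 44% and 29% for the three readings) shows the direction of the difference but does not predict this trial's result.

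The consequence is confined to one secondary endpoint. The correction should be made before analysis, but it does not threaten the trial's main conclusion.

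**What to change.** In Section 3.5, replace the condition with any detectable Day 28 spike antibody level, stating that levels of 250 U/mL or more are included. Use the same detectability convention that classifies patients as undetectable at baseline, so that baseline and Day 28 are judged alike. This wording agrees with the endpoint's label and with the durability bullet.

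If the authors did want the intermediate band, report Day 28 results in three levels: undetectable; detectable but below 250; and 250 U/mL or more. Either percentage can then be read from one table with one denominator.

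The cost is one sentence. Section 6.1.5 already provides the Day 14 and Day 28 measurements ("Anti-SARS-CoV-2 spike protein antibody and anti-SARS-CoV2 nucleocapsid total antibody levels will be obtained during these study event periods"), so no new data are needed, and the baseline classification and randomisation do not change.
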